#### **5.1.4. Handling of Missing Data for Adverse Events**

Missing data will not be imputed. Subjects who do not report an event will be considered as subjects without an event. The analysis of the solicited AEs will include only documented safety data (i.e. in case severity is missing it is not considered an event).

### 5.1.5. Solicited Local (Injection Site) Reactions

The analysis of local solicited adverse events will include:

1. Pain/Tenderness
2. Erythema
3. Induration/Swelling

### 5.1.6. Solicited Systemic Adverse Events

The analysis of systemic solicited adverse events will include:

1. Fever (defined as body temperature of 38.0°C or higher)
2. Headache
3. Fatigue
4. Myalgia
5. Nausea
6. Chills

## 5.2. Clinical Laboratory Tests

Any clinically relevant lab value measured from signing of the ICF onwards must be recorded on the adverse event page of the CRF and are analyzed as AE. The data will be summarized by the type of laboratory test.

In case a laboratory test result is *censored* (no numeric value is available, but only a verbatim term) then a numeric value will be imputed by a value preceding or exceeding the cut-off value with one unit. (<x: subtract 1 unit from x, >x: add 1 unit to x)

*Toxicity grades* will be determined according to the DAIDS Grading list (See also Appendix 1). In case no toxicity grades are defined for a test, the abnormalities (above/below normal range) will be used. In determining toxicity grades, the following rules are applied:

- worst grades/abnormalities are determined over the whole observational period for each trial phase separately, including all post-baseline measurements of that phase.
- The abnormalities ‘abnormally low’ and ‘abnormally high’ are considered equally important, i.e. if a subject has as well an abnormally low as an abnormally high value post-baseline, both abnormalities are shown in the tables. (This means that the sum of the percentages can be more than 100%)
- Note: as the grading scale for some parameters in the grading table has some gaps (zones where no toxicity grade definition exists), laboratory results falling in these zones will be allocated to the adjacent worst-case grade.
- If a lab value falls within the grading as specified in the grading table but also within the (local) lab normal limits, the value is considered as normal

***Definition emergent:*** An abnormality (toxicity grade or abnormality based on normal ranges) will be considered emergent in a particular phase if it is worse than the baseline (baseline = prior very first vaccination). If the baseline is missing, the abnormality is always considered as emergent. A shift from ‘abnormally low’ at baseline to ‘abnormally high’ post baseline (or vice versa) is also emergent.

### 5.2.1. Analysis methodology

Laboratory data will be analyzed based on the full analysis set. Unless specified otherwise, percentages are calculated versus the number of subjects in the analysis set with non-missing data for the parameter, period (if applicable) and treatment group under evaluation.

Tabulations of the worst graded abnormalities per period following vaccination will be provided. Grade 3 and 4 toxicities developed following vaccination will be listed. Tabulations of the worst emerging abnormalities (below/above) will be performed for tests that have no grading.

### 5.3. Vital Signs

#### 5.3.1. Definitions

Vital sign measurements will be performed at the time points indicated in the Time and Events Schedule (see CTP). Following parameters will be summarized:

- Temperature (°C)
- Blood Pressure: systolic/diastolic (mmHg)
- Pulse rate (bpm)

For definition of emergent refer to section 5.2.

#### 5.3.2. Analysis methodology

Any clinically relevant vital signs occurring from signing of the ICF onwards must be recorded on the adverse event page of the CRF and are analyzed as AEs. Tabulations of the parameters per period following vaccination will be provided. All findings will be listed by subject and by time point. Tabulations of the worst emerging abnormalities will be performed for parameters if applicable (see grading on Appendix 1).

Physical examination data will be listed.

## 6. IMMUNOGENICITY

### 6.1. Analysis specifications

The analysis of immunogenicity will be done on the PPI analysis set (Section 2.3). Data and timepoints from the subjects receiving the late boost vaccination will be reported also separated from the previous time points however the same rules defined for the main part of the study will be applied.

### 6.2. Immune Response Parameters

Humoral and cellular immune responses as measured by the following immune assays will be analyzed:

#### Humoral response

- Env ELISA IgG-t gp140
- ELISA IgG-1, IgG-3
- TZM-BL
- ADCP gp140
- BAMA IgG-3, IgG-t
- Ad26 VNA

#### Cellular response

- ELISpot
- ICS

### 6.3. Immune Response Analysis

No formal hypothesis on immunogenicity will be tested however at post-baseline timepoints the differences between the 2 active groups (Ad26.Mos4.HIV Clade C +Mosaic gp140/ Ad26.Mos.HIV + Clade C gp140) and the differences between the post-baseline timepoint (Week52 vs Week 28) within the same vaccine will be explored by means of a GMR including 95%CI and by a 2-sample t-test on the log data if those are normally distributed or by a Wilcoxon rank sum test otherwise. Those analyses will be performed on the following assays:

- ELISA: Clade C (C97ZA.012), Mos1, Clade B (1990a)
- ADCP: Clade C (C97ZA.012), Mos1, Clade B (1990a)
- ELISpot: Env peptide pool PTE, Gag peptide pool PTE, Pol peptide pool PTE, Env peptide pool Mos1

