An abbreviated, symptom-directed physical examination (including weight measurement) and measurement of vital signs will be performed for all subjects pre-vaccination. A urine pregnancy test must be performed before vaccination for women of childbearing potential, and results must be available and negative prior to vaccination. Pre-dose samples for hematology, biochemistry, HIV testing, and urinalysis will be collected. A pre-dose blood sample for the humoral immunogenicity assays will be drawn.

Pre- and post-dose AEs (including SAEs, AEs leading to treatment discontinuation, and AESIs of confirmed HIV infection) will also be collected, together with information about any concomitant medications.

Study vaccine will be prepared by the site pharmacist, who will place an overlay on the syringes (to preserve blinding) and will send it to the clinic. Administration of study vaccine to the subject can be performed by a qualified healthcare provider from the study site (including the pharmacist who prepared the study vaccine) who will have, on the day of administration, no other study function related to safety, study data evaluation or recording of AEs for those subjects that he/she vaccinated on that day.

After each vaccination, subjects will remain under observation at the study site for at least 30 minutes for presence of any acute reactions and solicited events (see Section 9.3), and vital signs measurement will be repeated.

Subjects will be provided with a thermometer, ruler, and subject diary to measure and record solicited events for 7 days post-vaccination (day of vaccination and the subsequent 7 days).

In addition to an HIV-risk assessment (see Attachment 2), counseling related to avoidance of HIV infection, pre- and post-HIV-test counseling, and contraceptive counseling will be provided to all subjects (men and women).

Subjects will complete a social impact questionnaire (Attachment 4).

Visit 8/Vaccination 3

The procedures for Visit 8 will be the same as at Visit 5 as detailed above. No social impact questionnaire will be completed.

Visit 13/Vaccination 4

The procedures for Visit 13 will be the same as at Visit 5 as detailed above.

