11.3. Sample Size Determination

The sample size in this study is regarded to be appropriate to assess the safety and tolerability of the different vaccine regimens. Placebo recipients are included for blinding and safety purposes and will provide control specimens for immunogenicity assays. With 25 individuals in a vaccine regimen, the observation of 0 such reactions would be associated with a 95% confidence that the true rate is less than 12%. For Group 2 with Mosaic and Clade C gp140 (n=100), there would be 95% confidence that the true rate is less than 3% when 0 events are observed. The following table shows the probabilities of observing at least one AE given true AE rates.

Probability of Observing at Least One AE in n Subjects

True AE Rate	n = 25	n = 100
0.1%	2%	9.5%
0.5%	12%	39%
1.0%	22%	63%
2.5%	47%	92%
5.0%	72%	99%
10.0%	93%	100%

The primary population for the safety analyses will consist of all subjects who received at least 1 dose (Ad26.Mos4.HIV or placebo).

Anticipating a dropout rate of approximately 10%, the sample sizes will allow detection of approximately 1.85-fold differences in Env-binding Ab titers, generally accepted to be biologically relevant, between the groups with Mosaic and Clade C gp140 (approximately 90 evaluable subjects) and their corresponding group with Clade C gp140 only (approximately 22 evaluable subjects); with 80% probability, assuming a 2-sided 5% Type I error and an SD of 0.4 on the log₁₀ scale.

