## 2. GENERAL ANALYSIS DEFINITIONS

A baseline (or reference) value will be defined as the value of the last available assessment performed prior to the first dose (active vaccine or placebo).

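### The Group 2 versus Group 1 comparisons after Week 24 leave a valid pre-divergence titre unused, giving up precision by an amount the documents do not fix

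*SAP*

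**What the plan says.** **Treatment.** Protocol Table 1 and the SAP's Definition of Terms give Ad26.Mos4.HIV alone to both active groups at Weeks 0 and 12. The groups first differ at Week 24, when Group 1 receives Clade C gp140 and Group 2 receives Clade C plus Mosaic gp140.

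**Sampling.** For Visit 5, Protocol 9.1.4 states: "A pre-dose blood sample for the humoral immunogenicity assays will be drawn". For Week 24 it adds: "The procedures for Visit 8 will be the same as at Visit 5 as detailed above". The Time and Events Schedule agrees, marking a pre-dose humoral sample at Visit 8. It marks no cellular sample at that visit; the last cellular draw before the groups diverge is at Week 16.

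**Analysis.** SAP 6.3 explores "the differences between the 2 active groups (Ad26.Mos4.HIV Clade C +Mosaic gp140/ Ad26.Mos.HIV + Clade C gp140") at post-baseline time points by GMR with 95% CI and a two-sample t-test on log data, or a Wilcoxon test if the data are not normal. The assays are ELISA, ADCP and ELISpot. Protocol 11.4 also plans unadjusted tests. Neither document names a covariate for this contrast, not even region, the randomization stratum. The only reference value is from before Dose 1: "A baseline (or reference) value will be defined as the value of the last available assessment performed prior to the first dose" (SAP 2). SAP 6.4 and 6.5 use baseline for fold increases and responder rules.

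The label for the Clade C group in the SAP 6.3 sentence (Ad26.Mos.HIV) differs from Table 1 and the Definition of Terms and should be reconciled with them.

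**The concern.** How well a subject responded to the two Ad26 primes is a natural candidate to predict the response after gp140. The Week 24 pre-dose value measures it. Although taken after randomization, it precedes any difference in treatment, and subjects and sites are still blinded (Protocol 5). Regimen therefore cannot affect it, and adjusting for it cannot remove part of the treatment effect.

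Any variation it explains is now left in the error term. This matters because Env-binding antibody is a primary endpoint, Week 28 is the primary analysis (Protocol 11.6), the sample size is justified on this contrast, and Group 1 has only about 22 evaluable subjects. Protocol 3.2 also shows how such estimates are used: regimen choice rested partly on GMRs with confidence intervals and on Clade C responses being judged comparable. Interval width bears directly on a judgement of that kind.

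**Working it through.** **Inputs (Protocol 11.3).** "assuming a 2-sided 5% Type I error and an SD of 0.4" on the log10 scale; power: "with 80% probability"; target: "approximately 1.85-fold differences in Env-binding Ab titers"; Group 2: "approximately 90 evaluable subjects"; Group 1: about 22.

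**Step 1: reproduce the plan's figure.**
- SE = 0.4 × √(1/22 + 1/90) = 0.4 × 0.2378 = 0.0951.
- Detectable difference = (1.960 + 0.8416) × 0.0951 = 0.2665 log10, and 10^0.2665 = 1.847.
- Power at 1.85-fold (0.2672 log10) is 80.2% by the normal approximation and 79.5% by the noncentral t.

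The stated 1.85-fold at 80% is confirmed without any adjustment.

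**Step 2: adjust for the Week 24 value.** With correlation rho between the Week 24 and the later log10 value, the residual SD is 0.4 × √(1 − rho²). So:
- detectable fold = 10^(0.2665 × √(1 − rho²))
- log-scale CI narrowing = 1 − √(1 − rho²)
- equivalent sample-size multiplier = 1/(1 − rho²)
- CI multiplier around the GMR = 10^(1.96 × 0.0951 × √(1 − rho²))

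The documents give no rho, so it is varied as an assumption:

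| rho | Residual SD | Detectable fold | Power at 1.85-fold | CI multiplier | CI narrowing | Sample-size equivalent |
|---|---|---|---|---|---|---|
| 0 | 0.400 | 1.85 | 80% | 1.54 | 0% | 1.00 |
| 0.2 | 0.392 | 1.82 | 82% | 1.52 | 2% | 1.04 |
| 0.3 | 0.382 | 1.80 | 84% | 1.51 | 5% | 1.10 |
| 0.5 | 0.346 | 1.70 | 90% | 1.45 | 13% | 1.33 |
| 0.7 | 0.286 | 1.55 | 98% | 1.36 | 29% | 1.96 |

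**Step 3: check by simulation** (20,000 trials per setting, 22 versus 90 subjects, normal log10 data). At a true 1.85-fold difference, ANCOVA power was 89.1% against 79.3% for the t-test at rho 0.5, and 97.2% against 79.7% at rho 0.7. With no difference, ANCOVA rejected in 4.7% to 5.1% of trials.

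**Step 4: availability of the covariate.** SAP 2.3.2 admits to the per-protocol immunogenicity set only subjects who had the third vaccination, so each of them attended the visit at which the sample is scheduled. The documents do not say that every listed ELISA and ADCP antigen was assayed at that visit.

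**The case against.** **No error is shown.** The two-sample analysis is valid, reaches its stated power and is labelled exploratory with no formal hypothesis. That stands, and it limits the point to efficiency. It does not make the interval width of a primary-endpoint GMR unimportant.

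**The covariate may be weak.** No correlation is given, and at rho 0.2 to 0.3 the gain is small. The sample comes 12 weeks after the second prime. How many values are then quantifiable is unknown, and the SAP 6.4 imputation at half the limit would weaken any correlation. This stands. A reader might infer that the Week 24 titre is a strong predictor, or that pre-Dose 1 values are nearly all below quantification. The documents show neither, and the SAP 6.5 responder rules provide for baselines at or above the limit.

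**It comes too late.** SAP 1 keeps the main-study text for completeness and will not rerun outputs up to Week 72. Protocol 3.2 already reports Week 52 GMRs. This stands against replacing the planned analysis now, which would raise a selective-reporting concern. It does not stand against an added, labelled estimate.

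**The decision data were already tighter.** The Week 52 GMRs in Protocol 3.2 pool this study with HPX2004. The Clade B interval of 1.7 to 2.7 implies a log10 SE of log10(2.7/1.7)/3.92 = 0.051. The Mos1 interval of 1.1 to 1.9 implies log10(1.9/1.1)/3.92 = 0.061. Both are below 0.0951 × 0.714 = 0.068, this study's value at rho 0.7. That is fair context, but it is a different analysis from the within-study contrast in SAP 6.3.

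**Conclusion.** The point holds as a modest loss of efficiency in the ELISA and ADCP comparisons of Groups 1 and 2 after Week 24, including Weeks 28 and 52. The gain from adjustment is minor at rho 0.2 to 0.3 (1.85-fold becomes 1.82 to 1.80). It becomes material at about rho 0.5 (1.70) and large at 0.7 (1.55). These figures assume the Protocol's SD of 0.4, 22 and 90 evaluable subjects, a linear relation on the log10 scale and a Week 24 result for nearly everyone.

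Two stronger readings are tempting and unsupported. One is that the planned GMRs are biased or underpowered: randomization makes the unadjusted comparison valid, and Step 1 confirms its power. The other is that the point covers every assay listed in SAP 6.3: ELISpot has no Week 24 sample.

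**What to change.** In SAP 6.3:
- Keep the planned unadjusted GMR and tests.
- Add, for log10 ELISA and ADCP values after Week 24, a Group 2/Group 1 GMR with 95% CI from an ANCOVA. The covariates are the Week 24 pre-dose log10 value of the same antigen and the region stratum. Apply the SAP 6.4 imputation to values below LLOQ or LOD.
- If an antigen was not assayed at Week 24, use Week 16 as the covariate for all subjects for that antigen. A subject-by-subject substitution would mix values from 4 and 12 weeks after the second dose.
- For ELISpot, allow a Week 16 covariate only as an optional sensitivity analysis.
- Label all adjusted estimates supplementary and post hoc.

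The cost is SAP wording and one extra analysis, with a few subjects lost to a missing covariate. No further enrolment or sampling is needed.

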11.4. Immunogenicity Analyses

Descriptive statistics (actual values and changes from reference) will be calculated for continuous parameters. Frequency tabulations will be calculated for discrete parameters. Graphical representations of changes in immunologic parameters will be made as applicable.

No formal hypothesis on immunogenicity will be tested. The analysis of immunogenicity will be done on the (per protocol) immunogenicity population as defined in Section 11.2.

Breadth of the binding Ab response will be summarized as the number of HIV clades to which a subject shows an Ab response. Magnitude and breadth of (n)Ab responses will be explored graphically through the generation of individual magnitude-breadth (M-B) curves. The area under the M-B curve (AUC) provides an overall summary of the M-B profile. The AUCs will be compared between groups using the Wilcoxon-Mann-Whitney test.

Differences between groups at a specific time point will be tested for exploratory purposes by a 2-sample t-test if the data appear to be normally distributed. If not, the non-parametric Wilcoxon rank sum test will be used. If portions of the measurements are censored below the assay

quantification limit, the Gehan-Wilcoxon test will be employed. All statistical tests will be 2-sided and will be considered statistically significant if p<0.05.

Frequency tabulations will be calculated for discrete (qualitative) immunologic parameters. Significant differences between groups will be determined by a 2-sided Fisher's exact test.

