## 1. INTRODUCTION

This statistical analysis plan (SAP) is applicable to all data available up to the end of the study.

The purpose of this document is to include the analyses for the late boost and the long term extension part of the study. For completeness, the description of the analyses regarding the data up to Week 72 are kept in this document but the outputs will not be repeated when data after Week 72 become available.

All the below described analyses are supposed to be performed on fully unblinded data.

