### **2.3.2. Per-Protocol Immunogenicity Analysis Set**

The per protocol immunogenicity (PPI) population consists of all subjects who have received at least the first three vaccinations, according to the protocol-specified vaccination schedule (+/- 2 weeks), have at least one measured post-dose blood sample collected and were not diagnosed with HIV during the study. Samples taken after Week 48 from subjects in the PPI population who missed the 4th vaccination or did not receive the 4th vaccination in the protocol-specified time window (+/- 2 weeks) will be excluded from the analysis.

The analysis of the immune responses will be performed on the per protocol immunogenicity population.

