### ICS

*T cells: CD4+, CD8+*

*Antigen: Combined pools and separated pools*

Cytokine counts: Marginal, Boolean AND (co-expression) counts, Boolean OR (and/or)

For CD4+ and CD8+ and for each antigen (combined and separated pools): n, median, quartile range, min, max, percentage of responders (see section 6.4) and corresponding 95% CI will be tabulated for each available cytokine background adjusted percentages listed below.

Cytokine (ISSCAT)	Description
CD154+	Marginal
GzB+	Marginal
ICOS+	Marginal
IFNg+	Marginal
IL2+	Marginal

IL17a+	Marginal
IL4+	Marginal
TNFa+	Marginal
IFNg+/IL2+	Boolean AND (co-expression)
IFNg+/IL2+/TNFa+	Boolean AND (co-expression)
IFNg+/TNFa+	Boolean AND (co-expression)
IL2+/TNFa+	Boolean AND (co-expression)
IFNg+ or IL2+	Boolean OR (and/or)
IFNg+ or IL2+ or TNFa+	Boolean OR (and/or)

Graphical presentations will be provided displaying dots for the subject values and including the median and the percentage of responders. In the graphs, original values will be displayed on the log10 scale.

The technical details for the calculation of the cytokine background adjusted percentages to be displayed in the above described outputs will be outlined in the DPS.

Additional timepoints and tests within one of the above listed assays may be investigated for exploratory purposes. Those data will be analyzed using the approaches described in this SAP.

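### SAP 6.3 applies two-sample tests to Week 52 versus Week 28 within a vaccine group, where the same subjects are measured twice and a paired analysis is needed

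*SAP*

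**What the plan says.** One sentence in SAP 6.3 covers two exploratory contrasts for ten readouts (three ELISA, three ADCP, four ELISpot). The first compares the two active groups at post-baseline timepoints. The second is within a group: "the differences between the post-baseline timepoint (Week52 vs Week 28) within the same vaccine will be explored by means of a GMR including 95%CI". A single test clause serves both: "by a 2-sample t-test on the log data if those are normally distributed or by a Wilcoxon rank sum test otherwise".

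Protocol 11.4 is narrower. It gives the two-sample t-test and the rank sum test only one use: "Differences between groups at a specific time point will be tested for exploratory purposes". The protocol does not plan the Week 52 versus Week 28 test; the SAP adds it.

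Three other SAP passages bear on the point:

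- Section 2.3.2 has an exclusion that begins "Samples taken after Week 48 from subjects in the PPI population who missed the" fourth vaccination, and extends to those vaccinated outside the window. Their Week 28 samples stay in the analysis.
- Section 6.1 says of the late-boost data that "the same rules defined for the main part of the study will be applied". Section 6.3, on additional timepoints and tests, ends "Those data will be analyzed using the approaches described in this SAP".
- Section 1 says of the analyses up to Week 72 that "the outputs will not be repeated when data after Week 72 become available".

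**The concern.** For Group 2 versus Group 1 the subjects are different people, and the named tests are suitable. For Week 52 versus Week 28 in one group, each subject contributes to both sides. A two-sample test computes the standard error as if the two sets of values were independent and ignores the within-subject covariance. The fallback is rank sum and not signed-rank, so the wording cannot be read as loose language for a paired test.

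This is the SAP's only tested contrast of what the fourth vaccination adds to the third. If the test is too conservative, a real rise or fall may be reported as not significant, most easily in the small Group 1.

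There is a second gap. The SAP does not say how the 95% interval of the within-group ratio is obtained. Because of the exclusion in section 2.3.2, an unpaired ratio can set a larger group of subjects at Week 28 against a smaller one at Week 52. That could move the point estimate as well as the p-value.

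**Working it through.** **Inputs.** Protocol 11.3 gives the SD ("assuming a 2-sided 5% Type I error and an SD of 0.4 on the log₁₀ scale") and about 90 evaluable subjects in Group 2 and 22 in Group 1. It gives the SD for Env-binding titers; no SD is given for ADCP or ELISpot. The correlation ρ between a subject's Week 28 and Week 52 log10 values is in neither document. It is assumed here, from 0 to 0.7, with the same SD at both visits and bivariate normal values.

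**The protocol's own figure.** Detectable between-group fold at 80% power = 10^(2.8016 × 0.4 × √(1/22 + 1/90)) = 10^0.2665 = 1.85. This reproduces the stated value.

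**Standard error.** The variance of the difference of two means on the same n subjects is 2 × 0.4² × (1 − ρ)/n. The two-sample method uses 2 × 0.4²/n. Its standard error, and the log-scale width of an interval built the same way, is therefore too large by 1/√(1 − ρ): 1.20 (ρ = 0.3), 1.41 (0.5) and 1.83 (0.7).

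**True size of the nominal 5% test.** In large samples this is 2 × [1 − Φ(1.96/√(1 − ρ))] = 1.9%, 0.56% and 0.03% at ρ = 0.3, 0.5 and 0.7. Simulated t-tests gave about 1.9%, 0.6% and 0.05% at n = 90, and 2.0%, 0.75% and 0.08% at n = 22. At ρ = 0 the size is 5%. At ρ = −0.3 it rises to 8.5%. The rank sum test behaves alike: at ρ = 0.5 its size is about 0.8% (n = 90) and 0.9% (n = 22).

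**Power, two-sample versus paired t-test (simulated).**

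| True fold | n | ρ = 0.3 | ρ = 0.5 | ρ = 0.7 |
|---|---|---|---|---|
| 1.3 | 90 | 47% v 62% | 47% v 76% | 46% v 93% |
| 1.3 | 22 | 11% v 19% | 8% v 25% | 4% v 38% |
| 1.5 | 90 | 88% v 94% | 92% v over 98% | 96% v 100% |
| 1.5 | 22 | 27% v 39% | 23% v 50% | 19% v 72% |
| 1.85 | 90 | over 99% for both | over 99% for both | over 99% for both |
| 1.85 | 22 | 60% v 71% | 61% v 85% | 64% v 97% |

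**Detectable fold at 80% power (normal approximation).** Two-sample: 10^((1.96 + 0.8416√(1 − ρ)) × 0.4 × √(2/n)). Paired: 10^(2.8016 × 0.4 × √(2(1 − ρ)/n)).

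| n | ρ = 0 | ρ = 0.3 | ρ = 0.5 | ρ = 0.7 |
|---|---|---|---|---|
| 90 | 1.47 for both | 1.44 v 1.38 | 1.42 v 1.31 | 1.39 v 1.23 |
| 22 | 2.18 for both | 2.10 v 1.92 | 2.03 v 1.73 | 1.96 v 1.53 |

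**The case against.** The strongest reply is that nothing decisional rests on this contrast. The SAP tests no formal hypothesis, the protocol has no objective on what the fourth dose adds to the third, and the regimen choice in Protocol 3.2 rests on between-group comparisons. With complete pairs the ratio itself is the same under either method, and geometric means and increases are tabulated by group and timepoint in any case. All of this stands, and it limits how serious the point is.

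The contrast is also largely retrospective. Outputs up to Week 72 will not be repeated, so rewording the sentence alone changes no Week 52 versus Week 28 result. This stands too, and is why a supplementary re-run is needed. The carry-over to later data is less certain: the SAP specifies no within-subject test for the late boost or the long-term extension. The between-group ELISA comparison named for the late boost suits a two-sample test. Sections 6.1 and 6.3 do, however, pass the present rules to any such test that is run.

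Finally, ρ is unknown, and folds of 1.3 and 1.5 are not protocol values. At 1.85-fold, which Protocol 11.3 treats as biologically relevant between groups, Group 2 loses essentially nothing. Group 1 still loses: 61% against 85% at ρ = 0.5. The t-test figures should not be carried over to ELISpot, which has no stated SD and is summarised by medians.

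**Conclusion.** The concern holds. SAP 6.3 assigns an independent-samples test to a within-subject comparison, and neither document supplies a paired alternative. Under positive correlation, the expected case for one subject's titers, the test is conservative and false positives do not increase. At ρ = 0 nothing is lost, and a negative ρ would reverse the direction.

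The material loss is in Group 1, at all three fold changes examined. In Group 2 it is confined to modest changes: large at 1.3-fold, small at 1.5-fold, absent at 1.85-fold. The sizes depend on the assumed ρ, an SD of 0.4 at both visits and normality, and apply to Env-binding titers. The interval inflation is conditional, because the method for the interval is not stated. The effect of unequal subject sets at the two visits has not been quantified. No between-group result and no confirmatory conclusion is affected. It should be corrected because the method is wrong as written and the remedy is cheap.

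**What to change.** Split the sentence in SAP 6.3.

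- **Between groups:** keep the two-sample t-test or rank sum test for Group 2 versus Group 1.
- **Within a group:** for Week 52 versus Week 28, and for any within-subject contrast of timepoints in the late-boost or long-term extension analyses, use subjects with both samples. Report the geometric mean of the within-subject ratios, with a 95% CI from the paired log10 differences, and a paired t-test or Wilcoxon signed-rank test. State the CI method. If Week 28-only subjects are to be kept, a repeated-measures model is the alternative.
- **Outputs already produced:** re-run the Week 52 versus Week 28 results for the ten listed readouts as a supplementary paired analysis, labelled as added after unblinding.

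The cost is one reworded SAP sentence and a small programming task. No new data are needed.
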